The PRP will be prepared following standard technique by drawing 60cc blood from the participant through venipuncture, and spinning the blood sample in a centrifuge (for approximately 17 minutes), adjusting for leukocyte poor-platelet rich plasma (LP-PRP). This sample will be prepared by the study provider (physician assistant or physician). Any leftover blood will be safely discarded per standard protocols.

A small portion of the injectant PRP (approximately 1 cc) will be sent to MAMC DPALS for complete blood count (CBC) cytology to monitor standardization and reproducibility. This portion will be labeled by participant ID and study. De-identified hardcopy results will be obtained from MAMC DPALS, and CBC results will be reported on Appendix G (CBC Results CRF).

PRP Injection:

PRP injection procedures will follow current clinical recommendation and standard operating procedures. Prior to the injection, the area will be sterilely prepared and anesthetized with either ethyl chloride spray or lidocaine (limited to the cutaneous and subcutaneous layer, so as not to alter the synovial contents). Then, the participant will receive LP-PRP injection in the affected knee area under ultrasound guidance. Qualified study providers will inject 2-5cc LP-PRP using an 18-gauge 1/5-inch needle for both aspiration and subsequent injection. Study providers will select the injection portal they are most comfortable with, in order to achieve an accurate intra-articular injection. The PRP injection procedure is expected to take approximately one hour.

One PRP injection is sufficient to observing the necessary clinical and molecular medicine outcomes.

Post-procedural instructions will be provided in a participant handout (Appendix Q).

SOC PT + Photobiomodulation Treatment (PBMT):

In addition to SOC PT, the PBMT group will receive PBM treatment, as outlined below.

PBM treatments will occur 3 times each week, for 3 weeks. A member of the study team will measure the treatment area according to a standard protocol and calculate the treatment time (approximately 5-20 minutes). PBMT will be delivered at 6 J/cm² and 25W and applied in a serpentine pattern to the knee area. Participants will be asked to refrain from using perfumes or plant extracts (e.g., St. John's Wort) in the treatment area(s), as this can increase skin photosensitivity.

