A self-report battery will be obtained using Appendix H Follow-Up Data Collection CRF, which will be administered at 3-weeks and 6-weeks post-intervention start.

A follow-up blood draw and synovial fluid aspiration will be completed at 6 weeks. The blood and synovial fluid samples will be processed by MAMC DCI staff as described in the "Sample Processing" section below.

Additionally, a chart review will be completed at 6 weeks to ensure that all related medical visit information is recorded in study documentation (Appendix I). A medical record review will be completed to obtain this information. A study visit is not required on behalf of the participant.

Participants will be evaluated for adverse events at each follow-up time point and any complications will be documented.

Data may be captured in person or remotely (e.g., entered directly into REDCap using a personalized coded link with no log-in required, verbally over the phone with a study team member, etc.). Reminder phone calls, texts, and/or emails will be sent to participants at their preferred contact method indicated on the Intake Form (Appendix B).

The Study Completion CRF (Appendix J) will be completed by a study team member to document the completion or withdrawal of all study participants.

Please see the Study Flow Diagram (Appendix L) for a visual representation of the study procedures.

Missed Appointments and Study Removal:

If a participant misses a scheduled appointment, they will be contacted to reschedule in order to maintain the treatment plan of their assigned study treatment group. In the event that a participant misses an appointment, study staff will make one attempt to reschedule each day on three separate days (for three total attempts to reschedule). If the participant cannot be reached or does not respond/reschedule, they will be removed from the study due to non-compliance.

Specimen Storage and Analysis:

All specimens will be collected, processed, and analyzed according to the recommendations of the respective manufacturer, current laboratory SOPs, or software recommendations. *When possible*, study staff will be blinded to treatment groups.

Molecular analyses will be performed over the following 6 months but may go on longer depending on the scope of assays performed, e.g. orthogonal validation.

Specimen Storage

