11.0 Statistical/Data Analysis Plan

11.1 Statistical Considerations:

List the statistical methods to be used to address the primary and secondary objectives, specific aims, and/or research hypotheses. Explain how missing data and outliers will be handled in the analysis. The analysis plan should be consistent with the study objectives. Include any sub-group analyses (e.g., gender or age group). Specify statistical methods and variables for each analysis. Describe how confounding variables will be controlled in the data analysis

This is an interventional and discovery-based protocol that will identify associations between molecular and demographic information and clinical outcomes.

Descriptive statistics will report location and scale in terms of mean and standard deviation for normally distributed variables, median and interquartile intervals for ordinal metric variables, and in terms of proportion and size for categorical variables. Descriptive statistics will be reported for baseline demographic and clinical characteristics at an overall level and by initial treatment group.

Outliers will be removed if determined to be erroneous based on relevant clinical expertise. Confounding will be principally controlled by randomization. In regards to the treatment of

missing data, subjects with missing baseline or 6-week follow-up data will be excluded from Aim 1 analyses regarding change from baseline to six weeks but will be included in Aim 2 analyses across all relevant time points.

Statistical methods

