11.5 Please provide a justification for your sample size

Since this is a discovery-based study of a novel topic, limited data are available with which to perform a power analysis. Thus we used a G*Power for a general comparison analysis without needing to root firmly in one specific variable.

If we are able to enroll 150 participants (a minimum of 92 post-attrition), assuming an effect size of .2, we will achieve 90% power. Effect size assumptions were taken from Tomazoni et al. 2016 based on the comparison of control versus PBMT with regards to biomarkers of gene expression that we assume to be an acceptable proxy for our primary comparison with regards to our biomarkers of concern. Significance threshold for power calculations was considered to be .01 to account for false discovery rate within our set of primary biomarker outcomes. Power calculations were performed using the WebPower package and the R Programming language.

11.6 Data Analysis Plan: Complete description: Background, Objectives, Design, Step by Step how the project is going to be done, Data analysis plan:

Aim 1 will be evaluated by comparing the PRP only and the PRP + PBMT treatment arms at six weeks relative to baseline. Generalized additive models predicting the fractional change in outcome measure at 6 weeks will be used.

Aim 2 will compare across all four treatment arms and will use Multi-Level models comparing the three treatment arms across time points and including random effects.

Aim 1 will include biomarker measures only; Secondary Aim 2 will include both biomarker measures and self-reports.

Hypothesis tests will be two-tailed and statistical significance will be considered at the putative threshold ($\alpha=0.05$). Any secondary P-values will be subject to a false discovery rate adjustment in keeping with best statistical practices. Multilevel models will incorporate random effects to account for repeated measures, using distribution families and link functions appropriate for the outcomes of interest, determined using QQ plots analyzed for best model fit. All statistical analyses will be performed using the R Programming language.

Clinical outcomes (pain scores) will be evaluated via ANOVA and post-hoc tests (Tukey's HSD test). A non-parametric alternative will be used if assumptions are not met.

Molecular Analyses:

DNA/RNA Analyses

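### Removal after a missed, unrescheduled appointment in effect drops the participant from Aim 1, and PRP+PBMT has up to eight more appointment days than PRP on which this can happen

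*Combined protocol and SAP*

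**What the plan says.** **Removal.** Under Missed Appointments and Study Removal (section 10.1), a participant who misses a scheduled appointment gets three rescheduling attempts, one on each of three days. The stated purpose is that "they will be contacted to reschedule in order to maintain the treatment plan of their assigned study treatment group". If this fails: "If the participant cannot be reached or does not respond/reschedule, they will be removed from the study due to non-compliance". A scheduled appointment is not defined in the text available, and Appendices K and L are not available to us.

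**Withdrawal.** Section 13.6 makes removal without the participant's consent a possibility, not a requirement, when someone does not adhere to the protocol or therapy plan. Its bar on further data collection after withdrawal stands under the participant's own withdrawal.

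**Outcome and analysis.** Section 10.1: "A follow-up blood draw and synovial fluid aspiration will be completed at 6 weeks". No other follow-up specimen is planned. Section 11.6: "Aim 1 will be evaluated by comparing the PRP only and the PRP + PBMT treatment arms at six weeks relative to baseline", on biomarkers only. Section 11.1: "subjects with missing baseline or 6-week follow-up data will be excluded from Aim 1 analyses regarding change from baseline to six weeks". The same section states: "Confounding will be principally controlled by randomization". For Aim 2, participants with missing data are kept, and section 11.6 "will use Multi-Level models comparing the three treatment arms across time points and including random effects".

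**Schedule.** Section 10.1: "PBM treatments will occur 3 times each week, for 3 weeks". Both Aim 1 arms receive one PRP injection. In the combined arm the first PBMT session falls on the injection day.

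**The concern.** No single sentence says that a removed participant leaves Aim 1, but the provisions together have that effect. Membership of the Aim 1 analysis set then depends on something that happens after randomisation, and the treatment under test creates the extra occasions on which it can happen. Randomisation is the plan's main control of confounding, and that protection weakens if the people removed differ in outcome from those kept.

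Some 6-week samples would also be lost from people who could still have given them, and a sample not taken cannot be recovered. The plan provides neither for outcomes after removal nor for a report of attrition by arm, so a reader of the results could not tell whether unequal loss had occurred.

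The sections also do not agree. Section 10.1 makes removal automatic, while section 13.6 leaves it to discretion. Whether the bar on data after withdrawal extends to people whom the study removes is not stated.

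**Working it through.** **Plan's own figure.** There is none on this point: the documents give no visit count by arm, no miss rate and no attrition by arm. The power statement in section 11.5 does not enter.

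**Step 1, the chain.** Missed and unrescheduled appointment leads to removal (10.1). Removal before week 6, with no provision for later sampling, means no follow-up biomarker (10.1). No 6-week value means exclusion from Aim 1 (11.1, 11.6). The rule adds to the loss only through appointments before week 6; someone who misses the 6-week visit itself is excluded anyway.

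**Step 2, extra days.** PBMT sessions = 3 per week × 3 weeks = 9. One shares the injection day, so PRP+PBMT has 9 − 1 = 8 more treatment days than PRP. Eight is an upper limit for appointment days, because PT, the 3-week visit or in-person check-ins may share a day with PBMT.

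**Step 3, illustrative size.** All of these inputs are assumptions: chance p of an unresolved miss per visit of 1%, 2% or 5%; independent visits; k visits before week 6; half of those removed still able to give a 6-week sample; removed participants differing from the rest by 0.5 SD, equally in both arms.

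- Removed = 1 − (1 − p)^k
- Loss due to the rule = 0.5 × removed
- Bias = 0.5 SD × (difference in loss between arms)

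Worked case, p = 2%, 5 vs 13 visits (four PT or 3-week visits common to both arms, plus 1 or 9 treatment days): removed = 1 − 0.98^5 = 0.096 and 1 − 0.98^13 = 0.231. Loss = 0.048 and 0.115, about 2.4 and 5.8 samples per 50 randomised. Bias = 0.5 × 0.067 = 0.034 SD.

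| Visits, PRP vs PRP+PBMT | Loss at p = 1% | Loss at p = 2% | Loss at p = 5% | Bias (SD) at 1%, 2%, 5% |
|---|---|---|---|---|
| 5 vs 13 | 2.5 vs 6.1% | 4.8 vs 11.5% | 11.3 vs 24.3% | 0.018, 0.034, 0.065 |
| 5 vs 9 (shared visits fall on PBMT days) | 2.5 vs 4.3% | 4.8 vs 8.3% | 11.3 vs 18.5% | 0.009, 0.018, 0.036 |
| 1 vs 9 (treatment days only) | 0.5 vs 4.3% | 1.0 vs 8.3% | 2.5 vs 18.5% | 0.019, 0.037, 0.080 |

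**Step 4, against precision.** The standard error of a two-arm difference at 30 per arm is √(2/30) = 0.258 SD. The largest bias is 0.080/0.258 = 0.31 of that; the worked case is 0.034/0.258 = 0.13.

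**Step 5, clustering.** Independence widens the contrast between arms, because unresolved misses plausibly fall on the same people. With a beta-binomial model and an assumed within-person correlation of 0.3, the worked case becomes loss of 3.0 vs 4.6% and bias of 0.008 SD. At p = 5%, bias is 0.019 SD for 5 vs 13 visits and 0.035 SD for 1 vs 9. With correlation 0.1 these three biases are 0.019, 0.039 and 0.058 SD.

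**The case against.** The strongest reply is that little is at stake. Every rate above is assumed, the direction is unknown, and the top figure needs a 5% unresolved-miss rate after reminders, weekly contact in every arm and three attempts. Out-of-window follow-up visits count only as minor deviations (section 16.1). Someone who cannot be reached gives no sample under any wording. The recoverable group is those who can be reached, will not rebook a PBMT session of about 5 to 20 minutes, yet would accept a blood draw and an aspiration; half is a guess. Enrolment is already inflated for attrition, the trial is described as discovery-based, and no intention-to-treat estimand is claimed for Aim 1. All of this stands, and it sets the priority low. It does not remove the unequal dependence on attendance: planned over-enrolment replaces numbers, not comparability, and in Aim 2 a removed participant adds only a baseline biomarker sample.

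It can also be said that multiple imputation for Aim 1 would add little. That is right. With only a baseline biomarker to work from, it does not repair outcome-related loss. In a large-sample simulation with loss of 11% vs 24% and a gap of about 0.5 SD, bias was 0.060 SD for complete cases, and 0.060, 0.056 and 0.045 SD after imputation at baseline correlations of 0, 0.3 and 0.5. The Aim 2 multilevel models, if fitted by likelihood, already rest on the same missing-at-random assumption.

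A reader might infer that section 13.6 forbids sampling a removed participant. The text does not go that far: the bar is written for people who choose to withdraw. Applying it to removal is an inference that nothing in the documents contradicts or confirms.

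**Conclusion.** The concern holds as a design weakness of low priority. As written, the removal rule reaches treatment sessions, in effect takes the participant out of Aim 1, and gives PRP+PBMT up to eight more days on which that can happen. Sections 10.1 and 13.6 must be reconciled.

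A reader might infer that Aim 1 will be materially biased, or biased in favour of one arm. The documents do not support that: they give no miss rate and nothing linking attendance to outcome. Under the assumptions shown, bias runs from about 0.01 to 0.08 SD with independent visits, below a third of a standard error throughout. It is smaller if misses cluster in the same people and zero if attendance is unrelated to outcome. A gap that differed between arms would change these figures, and the documents say nothing on that either.

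**What to change.** 1. **Section 10.1.** Record a missed, unrescheduled treatment session as non-adherence. Unless the participant withdraws, still invite them to the 3- and 6-week questionnaires (remote capture is already allowed) and to the 6-week blood and synovial samples.
2. **Section 13.6.** Reconcile it with section 10.1 on whether removal is automatic. State that non-adherence alone does not end outcome collection. Leave the other grounds for withdrawal and all treatment decisions unchanged.
3. **Sections 11.1 and 11.6.** Report attrition and its reasons by arm for Aim 1, from the completion form already planned (Appendix J). No imputation is requested.

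**Cost.** A protocol modification, possibly a consent check (the consent pages are not available to us), some extra contact with non-attenders, and one table. The 6-week sample includes an aspiration with stated minor risks (section 14.1), so it should be an invitation only. Keeping poor adherers may slightly dilute the estimated effect.

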PRP is postulated to increase chondrocyte proliferation, and increased collagen II and prostaglandin. Moreover, it may decrease apoptosis via insulin-like growth factor 1 (IGF-1). Inflammation reduction is also noted through regulated nuclear factor kappa B (NF- κ B), cyclooxygenase-2 (COX-2), and reducing IL-1 β and tumor necrosis factor-alpha (TNF- α) (Dhillon, 2017). PBMT acts in an anti-inflammatory mechanism by reducing mediators such as (TNF- α) (Hamblin, 2007) and anti-inflammatory mediators such as IL-10 (Peplow, 2011). Taken together, PRP acts through pathways, including inflammation reduction, which PBMT is shown to reduce. The combination of the adjunctive therapies may increase this ant-inflammatory cascade.

In knee OA rat models, PBMT has shown to decrease osteoarthritic degeneration, indicated by less irregularities in chondrocytes (Assis, 2016), higher thickness, and a better Osteoarthritis Research Society International (OARSI) score (Assis, 2018). Other animal studies showed that PBMT was the most effective at reducing expression of genes for enzymes that degrade cartilage as compared to other treatment modalities (Tomazoni, 2016, 2017). A recent meta-analysis confirmed these findings, indicating a positive effect of PBMT, as indicated by lower cartilage defect in animal knee OA models (Xiang, 2020). One study with human participants found PBMT in combination with exercise therapy could increase IL-10 levels, however, it was limited to women and only assessed a few biomarkers in this disease cascade (Vasso, 2021). Therefore, more work is necessary in human knee OA populations to understand the biological cascade of PBMT.

Preliminary rat model research has indicated the complementing properties of the combination of PRP and PBMT in acute rheumatoid arthritis (Goncalves, 2021). This potential additive treatment approach offers an exciting opportunity to improve treatment interventions in this population. It, however, has not been applied in humans.

Given the relatively low risk of each of these treatments, and the debilitating nature of knee OA with the subsequent impact on military readiness, this potential pathway to management should be investigated, and the pathway by which this delay of degeneration occurs categorized with relevant biomarkers. This study will compare the effects of 1) standard PT treatment, and PT

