Prior to receiving their assigned study treatment, participants will complete a Demographics CRF (Appendix C) and a Baseline Data Collection CRF (Appendix D). These questionnaires collect relevant data including: personal demography, military and employment demography, injury demography, and medical history, Fitzpatrick Skin Phototype, and validated self-reports.

A blood draw and a knee joint aspiration for synovial fluid will be conducted at baseline to assess for orthobiologics related to knee OA management (A complete list can be found in Section 10.2). Blood and synovial fluid date collection will be documented on the Baseline Data Collection CRF (Appendix D).

Blood Collection:

All team members will be trained, specifically in the methods of blood collection, safety, laboratory requirements, and processing, appropriate for their role in this study. These individuals will complete all training required by the MAMC lab, which can include hazardous materials handling, and biohazard safety.

The specimen collected in this study will not be used for clinical purposes.

An adequate amount of peripheral blood (approximately 11 ml) will be drawn by an experienced phlebotomist on the research team following standard sterile techniques. Blood will be collected into the appropriate blood collection tubes:

1. K2/EDTA Blood Tube 1 at 4ml
2. Heparin Blood Tube 1 at 4ml
3. DNA/RNA Shield Blood Collection Tube 1 at 3ml

The blood sample will be labeled with a sample ID (different from the study ID) and study visit, and transported to MAMC Department of Clinic Investigation (DCI) for storage and processing. Any excess blood sample will be safely discarded per standard protocol. Ice will be utilized for transportation, when necessary.

The blood samples will be processed by the DCI staff as described in the "Sample Processing" section below.

Synovial Fluid Collection:

Synovial fluid will be collected by the study team, including Orthopedic Surgeons, Physician Assistants, and Physicians at 3 possible locations:

1. MAMC Orthopedic Clinic
2. MAMC Sports Medicine Clinic
3. MAMC Physical Medicine and Rehabilitation

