 - Blood sample will be transported at 4°C to MAMC DCI.
 - Once at DCI, samples will be aliquoted into cryovials (200-500ul each) and stored at -80°C.
 - At a later date, when a complete batch of samples are available, samples meant for genomic or transcriptomic analyses will be thawed at 4°C or room temperature and their nucleic acids will be extracted using a kit appropriate for the sample and nucleic acid type (e.g., Zymobiomics Microbial DNA extraction kit or Qiagen DNA and RNA extraction kits).
 - Extracted DNA and RNA will be stored at -80°C for later processing.
 - DNA or RNA extracts will be barcoded using the appropriate protocol (e.g., for 16S or RNA sequencing on the Illumina MiSeq) and processed according to the manufacturer's protocols or as needed following experimental optimization.

Once sufficient sampling has been met, batch analyses will be completed for the respective biomarkers of interest. Single sample analysis may also occur for optimization and preliminary results.

These assays will evaluate many matrix and immune markers that may include ADAMTS-4 & 5, MMP 7 & 9, TGF-B, Aggrecan, HYAL2, CRP, HA, CD14, CD16, and CD64.

Additional Info - MIRROR/USU:

This research study is being conducted as part of Musculoskeletal Injury Rehabilitation Research for Operational Readiness (MIRROR), which is based out of the Department of Physical Medicine & Rehabilitation (PM&R) at the Uniformed Services University (USU).

MIRROR is focused on advancing musculoskeletal injury (MSI) rehabilitative care within the military healthcare system in order to reduce the burden MSIs have on military readiness and to ultimately enhance the operational capabilities of the armed forces. MSIs affect approximately 800,000 service members annually and result in 25 million days of limited duty. These conditions are the primary reasons for medical discharge/downgrade and result in 34% of medical evacuations from theatre. MIRROR was developed as a means to study risk factors of common MSIs, generate prevention strategies, optimize treatments, and establish return-to-duty criteria that is based on scientific evidence rather than case-specific clinical judgment alone.

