- Defense and Veteran's Pain Rating Scale (DVPRS) basic will capture pain daily.
- Single Assessment Numeric Evaluation (SANE) will capture function daily.
- Activity and medication use will also be recorded in a self-report diary.

- Knee Injury and Osteoarthritis Outcome Score (KOOS) will capture knee symptoms and associated functional status at baseline, 3 weeks, and 6 weeks post-intervention.
- The Veterans Rand 12 Item Health Survey (VR-12) will capture overall functional and health status at baseline, 3 weeks, and 6 weeks post-intervention.

PRP CBC analysis results will be reported on Appendix G (CBC Results CRF).

A chart review will be conducted at the end of 6 weeks to capture all SOC/PT visits.

We will use protein expression quantification and genetic analysis to target specific biomarkers in the areas of inflammatory mediators, growth factors, and intra-articular, structural homeostasis mediators.

10.3 At any point in the study, will you request, use, or access health information in any form, including verbal, hard copy and electronic?

- Yes No

10.4 Review the definitions below and respond to the following two questions. If you are not sure of the answers, email [contact] for assistance. The *Military Health System (MHS)* is defined as all DoD health plans and DoD health care providers that are organized under the management authority of, or in the case of covered individual providers, assigned to or employed by, the Defense Health Agency (DHA), the Army, the Navy, or the Air Force. *MHS workforce members* are employees, volunteers, trainees, and other persons whose conduct, in the performance of work for the MHS, is under the direct control of the MHS, whether or not they are paid by the MHS. *MHS business associates* are persons or entities that provide a service to the MHS and require protected health information (PHI) to provide the service.

Are you an MHS workforce member?

- Yes, I am an MHS workforce member
 No, I am not an MHS workforce member

Are you an MHS business associate?

- Yes, I am an MHS business associate
 No, I am not an MHS business associate

10.5 Have you consulted with an MHS data expert to determine the data elements required for your study?

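### The plan does not guarantee a test of the anti-inflammatory reason for adding PBMT to PRP, and the biomarkers that carry Aim 1 are never named

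*Combined protocol and SAP*

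**What the plan says.** Section 9.2 (Background and Significance) links PRP to collagen II, prostaglandin, IGF-1, NF-kB, COX-2, IL-1beta and TNF-alpha. It links PBMT to TNF-alpha and to "anti-inflammatory mediators such as IL-10". It then gives the reason for combining them: "The combination of the adjunctive therapies may increase this ant-inflammatory cascade".

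Section 9.3 sets Aim 1 as the effect of PBMT on PRP, judged by inflammatory and reparative biomarkers in synovial fluid and serum. No analyte is named there.

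The only list of analytes is in Section 10.1, under specimen processing: "These assays will evaluate many matrix and immune markers that may include ADAMTS-4 & 5, MMP 7 & 9, TGF-B, Aggrecan, HYAL2, CRP", followed by HA, CD14, CD16 and CD64. Earlier in Section 10.1, where the baseline samples are described, the reader is told "A complete list can be found in Section 10.2". The text of Section 10.2 says only that the study will "target specific biomarkers in the areas of inflammatory mediators, growth factors, and intra-articular, structural homeostasis mediators". It also refers to Appendix K, a data collection schedule, which is not in the public file.

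Section 11.5 bases power on a significance level of 0.01, chosen to allow for false discovery within the primary biomarkers. Section 11.6 restricts Aim 1 to biomarker measures, sets two-tailed significance at 0.05, and applies a false discovery rate adjustment to secondary P-values. Section 11 names no analyte.

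**The concern.** Aim 1 rests entirely on biomarkers, and the stated reason for expecting PBMT to add to PRP is a stronger anti-inflammatory effect. If the cytokines behind that reason are not required assays, the trial could finish with nothing to say about that pathway, whichever way the other markers fall.

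The second risk is selection. The marker list is open and no primary set is fixed. Section 10.1 allows single-sample runs for preliminary results before the batch analysis, and staff handling specimens are blinded only where possible. The markers reported as carrying Aim 1 could therefore be settled after some results are known, with no multiplicity control stated for them.

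**Working it through.** **1. Names set side by side.**
- Section 9.2, PRP (7): collagen II, prostaglandin, IGF-1, NF-kB, COX-2, IL-1beta, TNF-alpha.
- Section 9.2, PBMT (2): TNF-alpha, IL-10. Distinct mediators: 7 + 2 - 1 = 8.
- Section 10.1 list (12): ADAMTS-4, ADAMTS-5, MMP 7, MMP 9, TGF-B, aggrecan, HYAL2, CRP, HA, CD14, CD16, CD64.
- Overlap: 0 of 8.

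**2. Do the classes in Section 10.2 close the gap?** CRP can stand as the inflammatory mediator, TGF-B as the growth factor, and aggrecan, the MMPs and ADAMTS-4/5 as the structural markers. The listed panel therefore meets all three classes without any of the eight mediators. RNA panels or sequencing might capture some of their transcripts, but Section 10.1 makes each platform optional.

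**3. The plan's own power figure.** Section 11.5 states 90% power with 92 evaluable participants, effect size 0.2 and alpha 0.01, without naming the effect metric. Reading 0.2 as f-squared with three groups (2 numerator df, 92 - 3 = 89 denominator df) gives noncentrality 0.2 x 92 = 18.4 and power 0.9007, which matches. N = 91 gives 0.8965, so 92 is the smallest N that reaches 90%. Reading 0.2 as Cohen's f in a one-way comparison of three groups gives 0.171. A repeated-measures reading with f = 0.2 can also reach about 90%, but only with an assumed within-person correlation. The f-squared reading is used below.

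**4. What 0.01 implies.** As a Bonferroni share, 0.05/5 = 0.01, so the threshold fits five primary tests. No set of five is named. If all 12 listed markers were primary (assumption), the share is 0.05/12 = 0.0042, power at N = 92 is 0.837, and 90% needs 106. If each were tested in synovial fluid and in blood (24 tests, assumption), the share is 0.05/24 = 0.0021, power is 0.776, and 90% needs 116.

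**5. False positives at the analysis threshold.** For m independent tests with no true effects, the chance of at least one false positive is 1 - (1 - alpha)^m.

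| m | each at 0.05 | each at 0.01 |
|---|---|---|
| 5 | 0.226 | 0.049 |
| 12 | 0.460 | 0.114 |
| 24 | 0.708 | 0.214 |

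The 0.05 column applies if Aim 1 P-values are primary and so fall outside the adjustment in Section 11.6.

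**The case against.** The best defence is that the list is illustrative. Its wording excludes nothing, Section 10.2 commits the study to inflammatory mediators and growth factors as classes, and the protocol calls itself discovery-based. That stands: the eight mediators are not ruled out. They are simply not required.

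The mechanism is also wider than those eight. Section 9.2 reports animal work in which PBMT lowered expression of genes for cartilage-degrading enzymes, and it credits PRP with shifting cartilage turnover through growth and nuclear factors. ADAMTS-4/5, MMP 7/9, aggrecan and TGF-B address that part, and CRP bears on inflammation in general. A reader might infer that the trial could end without testing its own mechanism, or that no Aim 1 result could count for or against the hypothesis. The documents do not support either reading; the gap is confined to the named anti-inflammatory pathway.

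A reader might also infer that the complete list does not exist. This cannot be shown, because Appendix K is not available. What can be shown is that the text of Section 10.2, the place to which the reader is sent, contains no analytes.

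Finally, adding markers has costs. The multiplex platform is one option among several. No document shows that the 200-500 uL aliquots suffice for extra assays. Samples obtained by the 10 ml saline lavage after a dry tap raise a dilution question, although that question applies equally to the soluble markers already listed. These points argue for a small, deliberate primary set. They do not justify leaving the set unnamed.

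**Conclusion.** The point holds as a gap in outcome specification with a specific consequence. None of the eight mediators in the combination rationale appears among the 12 named markers, TNF-alpha included, and no other text requires any of them. The plan as written can be satisfied without a TNF-alpha, IL-1beta or IL-10 result, so a test of the anti-inflammatory reason for adding PBMT is not guaranteed. The catabolic-enzyme, matrix and growth-factor part of the rationale is represented.

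Separately, the primary biomarker set behind the 0.01 used for power is undefined, and the analysis threshold is 0.05 with adjustment stated only for secondary P-values. The 46% to 71% range assumes 12 to 24 independent tests, each at 0.05, with no true effects. Positive correlation between markers would lower it, towards 5% if they were perfectly correlated. The number of tests is an assumption because the plan gives none.

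**What to change.** Before the first trial sample is assayed:

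1. Put the marker list in Section 10.2, giving the matrix (synovial fluid, plasma or cells) and the assay for each marker.
2. Keep the 12 listed markers. Add the rationale mediators that can be measured as soluble proteins: TNF-alpha, IL-1beta, IL-10, and IGF-1 for the reparative side. Give a reason for any of the eight left out.
3. Mark a small Aim 1 primary set of marker-matrix pairs that includes at least TNF-alpha. Treat the rest as secondary or exploratory.
4. Make the Aim 1 threshold in Section 11.6 match that set, either by using the 0.01 from Section 11.5 or by applying false discovery rate control across the set. State the size of the set in Section 11.5.

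The cost is reagents, some sample volume, and a few more tests in the multiplicity family. Keeping the primary set small limits the power loss shown for 12 or 24 tests. No visit, procedure or participant burden changes, because samples are already stored and assayed in batches.
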